## **Listing:**

- All relevant data, generally variables listed above
- General medical history
- Tobacco use
- Disease recurrence
- Specific disease history
- Clinical complaints

# 8.4 Extent of Exposure

Unless otherwise specified, the analysis of extent of exposure will be characterized according to the number of participants exposed, the duration of exposure, and the dose to which they were exposed. Analyses in this section will be performed on the All Treated population "as treated" as described in Section 7.2.

# 8.4.1 Study Therapy

#### **Summary:**

Unless otherwise specified, administration of study therapy will be summarized separately for BMS-986277 and nivolumab and presented by dose level and biomarker level; tabulations by part, cohort, and indications may also be performed, as appropriate.

• Number (%) of treated participants exposed for specified periods of time such as:

- **Part 1**: less than 2 weeks (lead-in period only), 2 weeks to 6 weeks (1 cycle), 6weeks to 14 weeks (up to 3 cycles), and more than 14 weeks (up to 6 cycles).
- Parts 2 and 3: less than 2 weeks (sequential dosing of BMS-986277 prior to nivolumab),
   2 weeks to 4 weeks (1 combination cycle), 4 weeks to 12 weeks (up to 3 cycles), and more than 12 weeks (nivolumab maintenance).
- For this analysis, the exposure period is defined as first dose of either study drug to last dose of either study drug and will be summarized as a treatment regimen (rather than separately).

Descriptive statistics will be provided for the following:

- Number of doses
- Duration of therapy
- Cumulative dose
- Relative dose intensity (RDI)
  - Categories: < 50%; 50 < 70%; 70 < 90%; 90 < 110%;  $\ge 110\%$

Details for the calculations of these parameters are presented in Table 6 and Table 7.

Table 6: Study Therapy Parameter Definition for Part 1

Parameter	BMS-986277	
Dosing Schedule per Protocol	Cycle 1: 2 week lead-in period followed by 4 week sequential dosing period	
	Cycles 2-6: sequential dosing every 4 weeks	
	If only 1 dose is administered: Duration of therapy (weeks) = 2 weeks	
Duration of Therapy	If more than 1 dose is administered: Duration of therapy (weeks) = (last dose date - first dose date + 24) / 7	
	(Note: 24 days is the time between Day 19 and Day 43)	
Dose	Dose (vp) is defined as total dose administered in vp/dose at each dosing date as collected on the CRF.	
Cumulative Dose	Cum dose (vp) is sum of the doses (vp) administered to a participant.	
	If only 1 dose is administered: RDI (%) = [cumulative dose (vp) / (planned* dose (vp)] x 100	
Relative Dose Intensity	If more than 1 dose is administered: RDI (%) = {cumulative dose (vp) / [(duration of therapy (weeks) x {planned* dose (vp) + 3 x number of cycles x planned* dose (vp)}) / (2 weeks + number of cycles x 4 weeks)]} x 100	

\*Planned dose is the assigned dose recorded on the CRF.

Parameter	BMS-986277	Nivolumab
Dosing Schedule per Protocol	Sequential dosing on Days 1, 3, and 5 in a 28 day cycle for up to 3 cycles	480 mg on Day 15 in a 28 day cycle for up to 26 cycles
Duration of Therapy	Duration of therapy (weeks) = (last dose date of BMS-986277 - first dose date of BMS-986277 + 24) / 7 (Note: 24 days is the time between Day 5 and Day 29)	Duration of therapy (weeks) = (last dose date of nivolumab - first dose date of nivolumab + 28) / 7
Dose	Dose (vp) is defined as total dose administered in vp/dose at each dosing date as collected on the CRF.	Dose (mg) is defined as total dose administered in mg at each dosing date as collected on the CRF.
Cumulative Dose	Cum dose (vp) is sum of the doses (vp) administered to a participant.	Cum dose (mg) is sum of the doses (mg) administered to a participant.
Relative Dose Intensity	RDI (%) = {cumulative dose (vp) / [(duration of therapy (weeks) x 3 x number of cycles x planned* dose (vp)) / (number of cycles x 4 weeks)]} x 100	RDI (%) = {cumulative dose (mg) / [(duration of therapy (weeks) x number of cycles x 480 mg) / (number of cycles x 4 weeks)]} x 100

Table 7: Study Therapy Parameter Definition for Parts 2 and 3

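### SAP Tables 6 and 7 overstate BMS-986277 relative dose intensity by about 2 to 6 points when the last dose is the first or second infusion of a cycle

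*SAP*

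**What the plan says.** SAP Section 8.4.1 (Study Therapy) summarises number of doses, duration of therapy, cumulative dose and RDI. RDI is also banded: "Categories: < 50%; 50 < 70%; 70 < 90%; 90 < 110"%, then 110% and above.

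For Parts 2 and 3, Table 7 gives the BMS-986277 schedule as "Sequential dosing on Days 1, 3, and 5 in a 28 day cycle for up to 3 cycles". Duration is "Duration of therapy (weeks) = (last dose date of BMS-986277 - first dose date of BMS-986277 + 24) / 7", with the explanation "Note: 24 days is the time between Day 5 and Day 29". The RDI denominator uses "duration of therapy (weeks) x 3 x number of cycles x planned* dose (vp)) / (number of cycles x 4 weeks".

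For Part 1, when more than one dose is given, Table 6 uses "Duration of therapy (weeks) = (last dose date - first dose date + 24) / 7" and explains it as "Note: 24 days is the time between Day 19 and Day 43". A participant with a single dose has a separate rule.

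For nivolumab, given once per cycle, Table 7 uses "Duration of therapy (weeks) = (last dose date of nivolumab - first dose date of nivolumab + 28) / 7".

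**The concern.** The two notes show the intention: duration should run to Day 1 of the next cycle (Day 29, or Day 43 after Part 1 Cycle 1). Adding 24 days does that only when the last dose was the third sequential infusion. If dosing ends at the first or second infusion on nominal days, duration stops 4 or 2 days before the cycle end. The planned dose for that time is then too small and RDI too large.

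The pattern is foreseeable. Protocol Section 7.4.1 requires permanent discontinuation for events meeting the DLT criteria, subject to the exceptions in Section 7.4.4, so some participants may stop within a three-infusion block. RDI is presented by dose level, and Part 2 starts with 3 to 6 participants per level (protocol Section 5.2). One participant in the wrong band is 17 to 33% of such a level.

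**Working it through.** **Inputs.** From SAP Table 7: three infusions per 28-day cycle on Days 1, 3 and 5; duration = (last - first + 24)/7 weeks. From Table 6: one lead-in dose plus three infusions per cycle; same constant. The bands are from Section 8.4.1. Each infusion is taken as the full planned dose.

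**Reproducing the constant.** 29 - 5 = 24 and 43 - 19 = 24, as the notes say.

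**Formula, Parts 2 and 3.** The number of cycles cancels, so with n full doses

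RDI = n / [((last - first + 24)/7) × 3/4].

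A complete cycle gives 3 / [(28/7) × 0.75] = 100%. Two and three complete cycles also give 100%.

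**Benchmark.** The comparison is the same formula with duration run to the end of the last started cycle. On schedule, this equals doses received divided by doses planned in the cycles started.

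| Parts 2-3 pattern (nominal days) | Days counted | RDI as written | To cycle end | Band changes? |
|---|---|---|---|---|
| D1 | 24 | 1/2.571 = 38.9% | 33.3% | no |
| D1, D3 | 26 | 2/2.786 = 71.8% | 66.7% | yes, 50-<70 to 70-<90 |
| D1, D5 | 28 | 2/3 = 66.7% | 66.7% | no |
| Full C1 + C2D1 | 52 | 4/5.571 = 71.8% | 66.7% | yes, 50-<70 to 70-<90 |
| D1, D3 in both cycles | 54 | 4/5.786 = 69.1% | 66.7% | no |
| Full C1 + C2D1, D3 | 54 | 5/5.786 = 86.4% | 83.3% | no |

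Under the SAP's three-cycle maximum, two more cases change band: 6 of 9 doses ending on C3D1 (exactly 70.0% against 66.7%), and 8 of 9 without C3D5 (91.1% against 88.9%). The current protocol allows two cycles of BMS-986277.

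**Actual days.** The protocol allows the Day 3 and Day 5 infusions within 7 days of Day 1 (Section 7.1.4.1). With two doses in one cycle, RDI by day of the second dose is: D2 74.7%, D3 71.8%, D4 69.1%, D5 66.7%, D6 64.4%, D7 62.2%, D8 60.2%. The 70% line is crossed only when the counted duration is at most 26.67 days, so only for D2 or D3.

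**Part 1.** With k cycles, RDI = n / [((last - first + 24)/7) × (1 + 3k)/(2 + 4k)].

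- D1, D15: 2 / [(38/7) × 4/6] = 55.3% against 50%.
- D1, D15, D17: 3 / [(40/7) × 4/6] = 78.75% against 75%.
- Full C1 + C2D1: 5 / [(66/7) × 7/10] = 75.8% against 71.4%.
- Full C1 + C2D1, D3: 6 / [(68/7) × 7/10] = 88.2% against 85.7%.

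None of these changes band.

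**Nivolumab.** With one dose per cycle and +28 days, on-schedule dosing gives 100% for 1, 2 or 26 doses.

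**The case against.** The strongest reply is that RDI is dose per unit time, not the share of doses received. The same number of doses at different times may properly give different intensities, so 71.8% against 69.1% for 4 of 6 doses does not prove an error. The dose-count view is already reported through number of doses and cumulative dose, and neither is affected. This stands as a caution about the benchmark, which is an assumption. It does not rescue the constant: the SAP's own notes set the end point at the next cycle's Day 1, and the formula misses that point when the last dose is an early infusion.

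A second reply is that simply running duration to the end of the last started cycle would hide real delay within a cycle. Doses on D1, D5 and D8 give 3 / [(31/7) × 0.75] = 90.3% now and would become 100%. That is correct, and the change below is built to avoid it.

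A reader might also infer that RDI is inflated for any incomplete last cycle, or that everyone with two thirds of the doses moves up a band. Neither holds: D1 with D5 gives exactly 66.7%, a second and last dose on D8 gives 60.2%, and D1 with D3 in both cycles stays in its band at 69.1%.

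**Conclusion.** The point holds as a narrow arithmetic fault. On nominal days, when the last BMS-986277 dose is the first or second infusion of a cycle, RDI is overstated by about 2 to 6 points in Parts 2 and 3 and by about 2.5 to 5 points in the Part 1 patterns checked. A band changes only in particular Parts 2 and 3 patterns. Under the current two-cycle limit and nominal days, these are D1 with D3 alone, and a full Cycle 1 with C2D1. The result assumes full doses at each infusion and the cycle end as the intended end point.

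It would be tempting to say that the error distorts the reading of safety. The documents do not support that: safety is presented by part and dose level (SAP Section 8.6), exposure-adjusted event rates have their own patient-year denominator (Section 8.6.8), and no decision rule uses RDI. The effect stays in the descriptive exposure tables and listings.

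Table 6's single-dose rule gives 100% to a participant who received only the lead-in dose. That is a separate convention, not a result of the 24-day constant.

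**What to change.** In Table 7, and in Table 6 when more than one dose is given, define BMS-986277 duration in weeks as

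[later of (last dose date + 24 days) and (date of first infusion of the last started three-infusion block + 28 days) - first dose date] / 7.

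Completed on-schedule cycles still give 100%. Cycles cut short on schedule give the planned fraction: D1 with D3 gives 2 / [(28/7) × 0.75] = 66.7%, and Part 1 D1 with D15 gives 2 / [(42/7) × 4/6] = 50%. Real delays still lower RDI: D1, D5, D8 stays at 90.3%.

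The cost is one extra derivation step, identifying the start of the last block. The change leaves the single-dose rule in Table 6 as it is; that rule can be reviewed in the same edit.

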#### **Listing:**

- Batch numbers
- Administration of study medication (including CRF records of study medication, infusion details, and dose changes)
- Derived parameters (number of doses, duration of therapy, cumulative dose, RDI)

# 8.4.2 Discontinuation of Study Therapy

Discontinuation of study therapy will be summarized separately for BMS-986277 and nivolumab and presented by dose level and biomarker level; tabulations by part, cohort, and indications may also be performed, as appropriate.

#### **Summary:**

• Number (%) of participants with discontinuation along with the reason(s)

#### **Listing:**

• Dose discontinuation and reason(s)

#### 8.4.3 Interruption or Delay of Study Therapy

Modification of study therapy will be summarized separately for BMS-986277 and nivolumab and presented by dose level and biomarker level; tabulations by part, cohort, and indications may also be performed, as appropriate.

These modifications are as reported by investigators on the CRF. In the event that there is a modification with a missing reason, a category for "Unknown" will be included in the tabulations.

\*Planned dose is the assigned dose recorded on the CRF.

#### **Summary:**

- Number (%) of participants with dose delay, interruption and IV rate reduction along with the reason(s)
  - Number (%) of participants with at least one dose delay along with the reason(s)\*
  - Number of dose delays per participant
  - Number (%) of participants with at least one interruption along with the reason(s)\*
  - Number of interruptions per participant
  - Duration of interruption\*
  - Number (%) of participants with at least one IV rate reduction along with the reason(s)\*
  - Number of IV rate reductions per participant
- \*More than one reason or one interruption per participant may be counted in these statistics

#### **Listing:**

• All relevant information on dose modification listed above

# 8.4.4 Prior and Concomitant Therapy

Prior and concomitant medications will be coded using the World Health Organization (WHO) Drug Dictionary.

Concomitant medications are defined as medications other than study medications which are taken at any time on-treatment, either with a start date on or after the initiation of study therapy, or with a start date prior to initiation of study therapy and continuing during the study therapy.

Prior and concomitant therapies are presented by dose level, biomarker level, and overall; tabulations by part, cohort, and indication may also be performed, as appropriate.

#### **Summary:**

- Any prior therapy (radiotherapy, surgery, or systemic cancer therapy)
- Prior radiotherapy (Y/N) and site of radiotherapy
- Prior surgery (Y/N)
  - Ovarian: Debulking surgery outcome
- Prior standard of care medication therapy (Y/N)
- Prior platinum based medication therapy (Y/N)
- Prior systemic cancer therapy (Y/N)
  - Regimen number\*
  - Setting of regimen\*
  - Line of therapy\*
  - Best response to regimen\*
- \*More than one prior systemic cancer therapy may be counted in these frequencies
- Premedications and postmedications (Y/N)

• Prior and concomitant medications (including related AEs and for prophylactic vaccination) (Y/N)

# **Listing:**

- All relevant information on prior and concomitant therapies listed above, along with dates/times, total daily dose, site of radiotherapy, type of surgery, and any other information collected on the CRFs
- Subsequent therapy (surgery, radiotherapy, systemic cancer therapy) that occurs after first dose of study drug

# 8.5 Efficacy

Efficacy analyses will be based on the endpoints defined in Sections 5.2.1, 5.3.1, and 5.3.2.

The primary efficacy analyses will be performed on the All Treated population for the final analysis. Efficacy analyses based on Response-evaluable and/or CD8 Biomarker Evaluable populations may be performed as supportive analyses, particularly if these populations differ substantially from the All Treated population. If the majority of the All Treated population is included in Response-evaluable and/or CD8 Biomarker Evaluable populations, limited efficacy analyses may be performed on those populations (eg, ORR). For interim analyses when the minimum follow-up period is less than sufficient to warrant adequate interpretation of the result, efficacy analyses may be performed on Response-evaluable Participants.

Time to event distributions (eg, PFS, OS, and DOR) will be estimated using Kaplan-Meier (K-M) techniques. When appropriate, the median along with 95% confidence interval (CI) will be estimated using the Brookmeyer and Crowley methodology (using log-log transformation for constructing the CIs). Rates at fixed timepoints (eg, PFSR at 24 weeks or OSR at 12 months) will be derived from the K-M estimate and corresponding 95% CI will be derived based on the Greenwood formula using log-log transform^8. Confidence intervals for binomial proportions will be derived using the Clopper-Pearson method.

If BICR data is available, certain analyses (eg, ORR) may be repeated using the BICR data and presented by the accepted record after adjudication, Radiologist 1, and Radiologist 2. To assess concordance between BICR and investigator assessments, BOR may be cross-tabulated for the All Treated population for the assessment type (Investigator vs. BICR). Concordance will be assessed using the Gamma statistic and/or the Kappa coefficient. The concordance rate of responders will be computed as the frequency with which Investigator and BICR agree on the classification of a participant as a responder/non-responder. The concordance rate of progressors may be assessed similarly.

Indications for which the primary efficacy analysis is being performed using RECIST 1.1 may also be analyzed using iRECIST, if data is available. Analyses for iRECIST endpoints will use the same statistical methods as the analyses for RECIST 1.1 endpoints.

# **Summary:**

The following will be summarized by part, dose level, cohort, indication, biomarker level, and overall.

- The ORR and DCR with corresponding 2-sided 95% CI based on the Clopper-Pearson method, along with each category of BOR.
  - For interim analyses or internal monitoring of efficacy before the final BOR can be determined, this table may be repeated with unconfirmed responses.
- The DOR with median (95% CI) and range (min, max) by K-M method. The number of participants still in response at the time of database lock will be indicated. This summary includes responders (BOR of CR or PR) only.
  - For interim analyses or internal monitoring of efficacy before the final BOR can be determined, this table may be repeated with unconfirmed responses.
- The PFS and OS with median (95% CI) and range (min, max) by K-M method.
- The PFSR at specified timepoints (eg, Week 8, 16, or 24) by K-M method.
- The OSR (eg, Month 3, 6, 9, or 12) by K-M method. If the number of participants at risk is too small (eg, <5 due to high censoring), OSR will not be presented.
  - The minimum follow-up will be reported. The minimum follow-up is defined as the time interval between the last participant's first treatment date and the clinical cut-off date.
  - The currentness of follow-up, defined as the time between last OS contact (ie, last known alive date or death date) and data cut-off date, will be summarized by part, dose level, cohort, indication, biomarker level, and overall. Participants who died before the data cut-off date will automatically have zero value for currentness of follow-up. For participants with last known alive date after the data cut-off date, they will have zero value for currentness of follow-up as well. The currentness of follow-up will be categorized based on the actual available data and will be described in each deliverable's DPP. An example of the categories are: 0 days, 0-3 months, 3-6 months, 6-9 months, 9-12 months and ≥ 12 months.
  - The extent of follow-up defined as the time between first dose and last known alive date (for participants who are alive) or death date (for participants who died) will be summarized descriptively (median, min, max) for all treated participants.
- The iORR with corresponding 2-sided 95% CI based on Clopper-Pearson method along with frequencies of participants in each category of iBOR (CR/iCR, PR/iPR, SD/iSD, iUPD, iCPD, NE)
  - The categories may also be split into their respective subcategories
- The iDCR with corresponding 2-sided 95% CI based on Clopper-Pearson method
- The iDOR with median (95% CI) and range (min, max) by K-M method. The number of participants still in response at the time of database lock will be indicated. This summary includes responders (iBOR of CR, iCR, PR, or iPR) only
- The iPFS with median (95% CI) and range (min, max) by K-M method
- The iPFSR at specified timepoints (eg, Week 8, 16, or 24) by K-M method

#### Figure:

• Percent change from baseline in target lesions over time (ie, spider plot)

- Best Change in baseline target lesions (ie, waterfall plot)
- These will also include tumor assessments after the RECIST 1.1-defined progression. Swimmer plot of time to response, DOR, and time on therapy for responders only
- K-M plot of DOR for participants with BOR of CR or PR only
- K-M plot of iDOR for participants with iBOR of CR, iCR, PR, or iPR only
- K-M plot of PFS
- K-M plot of iPFS
- K-M plot of OS

#### Listing:

The following will be listed by using the listing convention described in Section 8.1, unless otherwise specified in the DPP. Some iRECIST data may be combined with the RECIST 1.1 listings.

- Tumor lesion measurements, including categorizations (new lesion target or new lesion non-target) and measurements for new lesions)
- Tumor evaluation at each visit, including non-target lesions and new lesions, tumor change from smallest sum of diameters in target lesions, corresponding change (or percent change) from baseline, a symbol denoting the index iUPD visit, and change from iUPD visit
- Participant level efficacy per RECIST 1.1/PCWG3 for all treated participants, including tumor best overall response (BOR), maximum response in tumor burden, PFS, death indicator
- For responders per RECIST 1.1/PCWG3: BOR, time on therapy, DOR, response duration after treatment discontinuation, reason for treatment discontinuation
- Participant level data for endpoint determination per iRECIST, including death date, iDOP, date of clinical progression, date of subsequent therapy, date of last evaluable scan prior to subsequent therapy, date of last evaluable scan, and the end date of the evaluable period
- Participant level efficacy per iRECIST for all treated participants, including tumor immune best overall response (iBOR), maximum response in tumor burden (including tumor assessments after the RECIST 1.1-defined progression), iPFS, death/censoring indicator
- For responders per iRECIST (iBOR of CR, iCR, PR, or iPR) iBOR, time on therapy, iDOR, response duration after treatment discontinuation, response duration after index iUPD, reason for treatment discontinuation
- Survival survival status, first dose date, last dose date, last known alive date, death date, time to death

# 8.5.1 Other Observations Related to Efficacy

Additional exploratory efficacy analysis may be performed if deemed appropriate by the study team, provided there is sufficient data. These will be detailed in the DPP. Examples include, but are not limited to:

- Summary measures and corresponding plots of indication-specific efficacy biomarkers such as:
  - PRC: absolute PSA and PSA doubling time

CRC: CEA

Ovarian: CA125PC: CA19-9

 Efficacy by clinically meaningful disease characteristics such as prior therapy or mutation status

# 8.6 Safety

Analysis of safety will be based on the All Treated population and presented by part, dose level, and overall; tabulations by cohort, indication, and biomarker level may also be performed, as appropriate. Deaths and SAEs will be listed using the All Enrolled population. The treatment groups will be "as treated" as defined in Section 7.2.

Adverse events will be coded according to the most current version of MedDRA at the time of each database lock and the severity will be graded using the NCI CTCAE version 4.03. Treatment-related AEs are those events with relationship to study treatment "Related" as recorded on the CRF. If the relationship to study treatment is missing, the AE will be considered as treatment related.

Listing of AEs will include all enrolled participants, as SAEs and deaths are collected pretreatment. Summaries of AEs will include (1) events occurring from the first dose date to 30 or 100 days (inclusive) after the last dose of either study treatment for Part 1 or Parts 2-3, respectively, for participants who are off study treatment and (2) all events occurring from first dose date for participants who are still on study medication.

Unless otherwise specified, the AE summary tables will be restricted to on-treatment events regardless of the causality. AEs and treatment-related AEs will be tabulated by descending frequency of system organ class (SOC) and descending frequency of preferred term (PT) within each SOC, unless otherwise specified. When reporting AEs by CTC grade, summary tables will be provided based on the event with the worst CTC grade (independent of relationship to study medication). Participants will only be counted (1) once at the PT level, (2) once at the SOC level, and (3) once in the 'Total participant' row at their worst CTC grade, regardless of SOC or PT.

The analysis of laboratory results will be based on the All Treated population with available data. Laboratory results will be categorized according to NCI CTCAE version 4.03 grade. Baseline is defined in Section 7.1.1. Summaries of laboratory results include baseline and (1) post-baseline results up to 100 days (inclusive) after the last dose of either study treatment for participants who are off study treatment and (2) all available post-baseline results for participants who are still on study medication.

